16.5 Analyses

We will use an intention to treat approach in all our primary analyses. A per protocol analysis will be undertaken if substantial deviations from the allocated treatment or a substantial amount of missing values are observed. In all cases the per protocol analyses will serve as a "sensitivity analysis" as intended by the ICH9 guidelines and a further support for proper interpretation of the ITT conclusions.

Patients switching to steroids will be withdrawn from further data collection but are retained in the study as such. Their MAF will be included up to the time they started the new medication.

Apart from the primary analyses which focus on a specific time point (6 months), secondary analyses will take the full repeated measurements structure into account, including the 6 months values. We use a mixed model for repeated measurements with time since randomisation as a fixed covariate (or factor), lnMAF0 as a

continuous covariate and Treat as a fixed factor. We will apply an AR1 covariance structure unless the data prove this to be untenable. This model is a direct extension of the simple regression model used to test the primary hypotheses and allows estimation of treatment effect over time, including possible interactions. We will also analyze the data using generalized estimating equations (GEE), aiming to consolidate the results from the mixed model analysis.

The mixed model will take the missing values into account in a natural way, assuming of course missingness at random. A sensitivity analysis will be undertaken to verify this assumption.

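### The secondary repeated-measures model defaults to AR1 with no switching criterion, no named replacement and no robust standard error

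*Combined protocol and SAP*

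**What the plan says.** The primary analysis (16.2) is a regression of lnMAF6 on lnMAF0 and Treat at a single time point. Section 16.5 then adds that "secondary analyses will take the full repeated measurements structure into account, including the 6 months values". The fixed effects are time since randomisation, lnMAF0 as a "continuous covariate and Treat as a fixed factor". Interactions are mentioned only as possible. No patient random effect is named.

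On covariance there is one sentence: "We will apply an AR1 covariance structure unless the data prove this to be untenable". What would count as untenable, and what would replace AR1, is not stated.

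On the companion analysis: "We will also analyze the data using generalized estimating equations (GEE), aiming to consolidate the results from the mixed model analysis". No working correlation or type of standard error is given.

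On missing data: "The mixed model will take the missing values into account in a natural way, assuming of course missingness at random", followed by "A sensitivity analysis will be undertaken to verify this assumption". One source of missing data is explicit: "Patients switching to steroids will be withdrawn from further data collection but are retained in the study as such".

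Section 7.2 lists the MAF of every 4-week period over the whole follow-up as a secondary endpoint.

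**The concern.** AR1 makes the correlation between two periods decay geometrically with the gap between them. A lasting difference between patients does not decay. If such differences remain after adjustment for lnMAF0, AR1 treats a patient's later periods as more nearly new information than they are. The model-based standard error of an effect averaged over periods is then too small.

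Persistent differences are plausible here. Section 2.5 describes 14 treated patients whose improvement ranged from 90% or more in three to none in the four not counted as improved. Variation in response arises after baseline, so lnMAF0 cannot absorb it.

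At stake is the secondary estimate of the treatment effect over the blinded phase. In addition, a likelihood analysis under missingness at random relies on a correct covariance, so the covariance choice also bears on the claim that missing values are handled naturally.

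**Working it through.** **1. The plan's own figures (16.4).** The documents give no figure for the AR1 model; the nearest is the power of test (2c). With 60 per arm, difference 0.42 and SD 0.54, the noncentrality is (0.42/0.54) × √(60/2) = 4.26. Two-sided power at 5% is 98.8% (noncentral t) against the stated 98%. This test does not use AR1.

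**2. What 16.4 implies about correlation.** With equal SDs of 0.54, corr(lnMAF0, lnMAF6) = 1 − SD(Delta)²/(2 × 0.54²). SD(Delta) = 0.54 gives 0.50; 0.76 gives about 0.01. If correlation ρ is constant over time, the residual correlation after adjusting for lnMAF0 is ρ/(1+ρ), at most 0.50/1.50 = 0.33. A persistent response effect arising after implantation could raise it; the documents give no figure.

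**3. Size of the averaged Treat test, worked case.** Assume residual correlation 1/3 between all periods and T = 6. The fitted AR1 parameter converges to r = 1/3.
- Model-based variance, in units of residual variance: 1/(1′R⁻¹1), where 1′R⁻¹1 = [T − (T−2)r]/(1+r) = (6 − 4/3)/(4/3) = 3.5. This gives 0.2857.
- AR1 weights are proportional to 0.75 for the two end periods and 0.50 for the four interior ones. Normalised, they are 0.2143 and 0.1429, with sum of squares 0.1735.
- True variance: (2/3)(0.1735) + 1/3 = 0.4490.
- Ratio of true to model standard error: √(0.4490/0.2857) = 1.254.
- True size: 2[1 − Φ(1.96/1.254)] = 11.8%.

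**4. Other patterns.** These use the same large-sample method. The patient share of variance (assumed 0.5–0.8) and the lag-1 correlation of the remaining noise are assumptions, because the documents give neither.

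| Noise correlation | 6 periods | 12 periods |
|---|---|---|
| 0 | 11.8–12.1% | 21.9–22.3% |
| 0.3 | 8.2–8.4% | 14.6–15.3% |
| 0.6 | 5.7–5.8% | 8.5–8.8% |
| Pure AR1, monthly correlation 0.89 | about 4.5% | about 4.5% |

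The last row matters because 0.89⁶ ≈ 0.50. The upper end of the correlation range in 16.4 is therefore equally compatible with AR1.

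**5. Simulation, 60 per arm, six periods, AR1 fitted by REML.** With 3,000 runs per cell, patient share 0.5 and noise correlation 0, 0.3 and 0.6, size was 11.8%, 8.8% and 5.0%. With share 0.8 and independent noise it was 12.8%. A separate simulation of 300–500 runs per cell gave about 13–14% under pure persistence, including at residual correlation 0.33. In the 3,000-run cells a robust standard error brought size to 4.6–5.9%.

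**6. Month-6 contrast.** With treatment by time in the model and complete data, this contrast depends on the month-6 variance rather than on the correlations. Under pure persistence the ratio of true to model standard error is 1.00, so there is no inflation.

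**7. Drop-out bias.** Large-sample simulation (60,000 per arm), month-6 effect about −0.42.
- Drop-out following high recent or mean attack frequency by the same rule in both arms (15–26% lost per arm): AR1 gives −0.411 to −0.415 against full-data −0.416 to −0.426, a bias of about 0.00–0.01.
- Drop-out in opposite directions by arm (23–24% against 40–43% lost): AR1 gives −0.33 to −0.37, while compound symmetry gives −0.42 to −0.43.
- A separate arm-dependent simulation with 18–28% drop-out gave a bias of −0.04 to −0.12, so the direction depends on the mechanism.

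**The case against.** The strongest reply is that AR1 is only a default. Every inflation figure above forces AR1 regardless of fit, whereas 16.5 lets the data overrule it. Taking AIC as an assumed criterion with patient random intercept plus AR1 as the alternative, AIC preferred the alternative in 100% of 400 simulated trials in each six-period setting with size above 8%. In separate runs of the full procedure it switched in 91–100% of trials, and size came back to about 4–7% over six periods. This stands, and it rules out the inference that the plan as written will report a false dose effect over time. It does not close the gap: neither AIC nor that alternative is in the plan, and where size is about 5.7% the switch occurs in only 41% of trials.

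Other stronger readings are also unsupported:
- *The main result is at risk.* The model is secondary. The primary regression, the closed testing procedure and the sample size do not involve it.
- *Error rates above 20% apply.* Those belong to a Treat effect pooled over 12 periods, which mixes in the open extension. The plan names no such pooled test.
- *Protection under missingness at random is lost.* True in principle, but usually negligible in size. The plan also promises a sensitivity analysis, and the GEE uses drop-outs' data too.
- *The GEE cannot help.* Robust standard errors would restore the size; the plan simply does not state them. What unweighted GEE does not supply is validity under missingness at random.

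**Conclusion.** The point holds as a gap in specification for a secondary analysis. AR1 alone is a fragile default for monthly attack rates, and its one safeguard leaves both the trigger and the replacement to be decided after the data are seen. If AR1 were retained under persistent residual patient differences, the nominal 5% test of the Treat main effect over the six blinded periods would have a size of roughly 8–14%. This rests on assumed within-patient correlations, model-based standard errors and a Treat effect averaged over periods. The size is about 6% with strong short-range correlation and nominal if AR1 is true; the documents do not show which case applies. Drop-out bias is a minor part of the point unless drop-out depends strongly on arm.

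**What to change.** Replace the AR1 sentence in 16.5 with: *Unstructured covariance with Kenward-Roger degrees of freedom for the six blinded 4-week periods; if it does not converge, patient random intercept plus AR1 with robust SE.* Use the fallback structure for any model over the whole follow-up, where an unstructured matrix for 12 periods would need 12 × 13/2 = 78 parameters. State robust standard errors for the GEE. Inverse-probability weighting of the GEE is optional.

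The change is to analysis-plan wording only. The cost is more covariance parameters (6 × 7/2 = 21 instead of 2 for AR1) and a possible convergence fallback. No data collection, sample size or primary analysis changes.

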16.6 Randomisation and blinding

Patients are randomised using a variable blocked stratified balanced design. The entire randomisation is generated before the first patient enters the trial and fixed. The randomisation table, although stored with the trial data base, is not accessible by users of the data management system except for the trial statistician and the implanter and casemanager. When a patient is entered into the (web based) data management system, the eligibility criteria are checked and the required stratification variables are specified. A request for randomisation is generated by the system and the next available record with the correct stratification values in the hidden randomisation table is allocated to the patient; both patient and randomisation record have a unique key which is stored both in the data tables and in the randomisation table. In the clinical data base the fact that the patient has been randomised, is made known by storing a random key which points to the record in the randomisation table. However, the web based interface does not allow any data manager or clinician to see the randomisation result if not authorized so by the very design of the trial. When the study data have to be analyzed according to randomised treatment, the randomisation table can be extracted from the data base by the statistician and joined to the clinical data extracted by the data manager of the trial. In case of emergency the statistician or implanter can either log on to the system and

retrieve the randomisation of a patient via his (authorized) account or the randomisation table can be viewed directly in case the internet connections break down (but only from within the dep. of Medical Statistics). A backup of the Protocol: Occipital nerve stimulation in medically intractable, chronic cluster headache CME Protocol number: 10.016 Version 1.11 dd. 26-09-2018 randomisation table is by definition assured since the entire data base is back up every day.

17. Risk assessment

ONS most important, known, related risks include: lead migration , low battery, neck stiffness (45). The risk of lead migration is probably related to the surgery technique used. In a recent Dutch study in 4 patients treated with ONS, there was no lead migration (unpublished data) or any other complications after 1.5 year follow-up. Other possible complications are unpleasant sensations of paraesthesias, haematoma, limited neck movements, skin discomfort, hardware failure (e.g. early end of life of the battery, which can cause sudden increase of headache) and infection.

Treatment-as-usual related risks are related to the medication used and do not increase due to participation in this study.

Until now, no persistent iatrogenic neurological deficit has been reported using ONS.

Low Battery

A low battery has to be surgically replaced. This will eventually occur in all patients, so it can be debated if an empty battery must be considered as a complication.

18. Investigator / Site Selection

18.1 Implantation site

Site selection for implantation will be based on experience with and interest in ONS therapy for headache. Sites will be located in The Netherlands, UK and Denmark and probably Germany and Belgium.

In order to qualify for participation in the study, sites are required to meet the following criteria:

1. Willing to comply with the Clinical Investigation Plan (CIP), all required procedures, the Declaration of Helsinki and local regulations

2. Expertise in chronic pain treatment with ONS therapy and programming the stimulator

3. Availability of physician programmer (N'Vision) to adapt the ONS programming parameters

18.2 Patient recruitment site

Site selection for recruitment will be based on experience with treating CCH. Sites will be located in Europe. The investigator must have sufficient time to address the study requirements, reporting requirements and must have experience in patient selection and management. There must be a patient recruitment potential of at least 4 - 8 CCH patients/year for the trial.

18.3 Training requirements

The following will be addressed prior to site activation and throughout the study as needed:

- Protocol specific training
- Study training relevant and pertinent to the involvement of personnel conducting study activities, including investigator responsibilities
- Product-specific information/device training
- Specifics of study conduct
- AE reporting

The site and sponsor will maintain documentation of attendance at each of these training opportunities.

19. Study Organization

Study Management

Protocol: Occipital nerve stimulation in medically intractable, chronic cluster headache CME Protocol number: 10.016 Version 1.11 dd. 26-09-2018 The study will be managed and coordinated by the Leiden University Medical Centre,

Leiden, The Netherlands.

Study Investigators

19.3 Amendment Procedure

Any amendment to the Clinical Investigation Plan will be agreed by Coordinating Clinical Investigator and Principal Investigator prior to submission to Ethics Committee and Competent Authorities if applicable.

19.4 Boards

The Steering Committee will monitor the study and review its progress at regular intervals. Based on these reviews and Data Safety Monitoring Board (DSMB) outcomes, the Committee may request that the study be put on hold or even terminated for safety, ethical or other reasons.

An independent DSMB will be established prior to study enrolment and will have a minimum of three members with relevant expertise, and experience in clinical studies and/or as a DSMB member for another study. All members will lack significant conflicts of interest and one will be a biostatistician knowledgeable in the area of statistical methods used for clinical studies. One DSMB member with previous experience will be appointed as the chairperson.

A DSMB Charter (or Manual of Operations) will be developed and agreed upon by the Sponsor and all DSMB members prior to the review of study related data. The Charter will describe its functions including, but not limited to, the following:

- Meeting schedule and format
- How the confidentiality/blinding of the data will be maintained
- Who may attend all or part of the meetings
- How conflicts of interest for potential committee members will be assessed
- Timing and format for the presentation of data to the DSMB
- How recommendations will be communicated to the Sponsor
- Definition of a quorum
- Interim and final analysis
- Parameters for early termination
- Procedures for documenting meeting minutes
- Maintenance of relevant records

The DSMB will receive summaries of adverse events reports on a bi-annual basis. The board may meet after bi-annual review, if they believe it is necessary. However, the DSMB will be convened at least once a year, and additional meeting may be scheduled based on the accumulation rate of data on safety and effectiveness.

20. Ethical Basis

This study has been designed and shall be conducted according to the principles set in the Declaration of Helsinki 2008 revision and Good Clinical Practice (GCP)

Appropriate Ethics Committees approval for the study and the patient information sheet and consent form will be required prior to beginning the study. A copy of the approval is required by the LUMC prior to the first investigational product being implanted.

21. Insurance / Indemnification

Each participating centre maintains appropriate clinical trial liability insurance coverage as required under applicable laws and regulations and will comply with applicable local law and custom concerning specific insurance coverage. If required, a Clinical Trial insurance statement/certificate will be provided to the Ethics Committee for each individual participating recruitment or implantation centre. Indemnification statements will be provided as required per regulations.

22. Publication Policy

This study will be registered in a secured database in accordance with the Declaration of Helsinki, and data resulting from the study will be made publicly available. It is anticipated that at least one publication will be generated from the study results, to be published in a peer reviewed journal. The principle investigators will have access to all cleaned study data and can use it for scientific purposes. The investigators can propose projects to the principle investigators using the database.

With respect tot publication policy, the following aspects will be addressed:

- 1. All study results will be published without restrictions. This means that patients are entitled to the right that the study results will be published, based on their participation in the study.
- 2. All members of the study group agree that all study results will be published.
- 3. Both negative and positive results will be published.
- 4. Before publication, all authors will have the opportunity to give comments on the manuscript.
- 5. Data will be published as soon as possible after finishing data analysis.

Specific details will be described in a separate publication plan, which will be provided to investigators for review and agreement.

23. Study reimbursement

